#### 10.6.1.2 Adverse Event Rating and Reporting

All events plausibly related to insomnia, insomnia treatment, suicidal ideation, or any study procedure will be promptly rated using the anticipation, severity, and attribution scales below. These ratings will be included in the Case Report Form for the adverse event and signed by [name] or [name].

##### Anticipation

1. Anticipated
2. Unanticipated

##### Severity

1. Mild: Awareness of sign or symptom but easily tolerated
2. Moderate: Interference with normal daily activities
3. Severe: Inability to perform normal daily activities
4. Life-Threatening: Immediate risk of death from the reaction as it occurred

##### Attribution

1. Definite: Adverse event clearly related to study involvement
2. Probable: Adverse event likely related to study involvement
3. Possible: Adverse event may be related to study involvement
4. Unlikely: Adverse event doubtfully related to study involvement
5. Unrelated: Adverse event clearly not related to study involvement

All AEs that meet the IU IRB prompt reporting requirements (unanticipated; definitely, probably, or possibly related to study involvement; and suggest that the research places participants or others at a greater risk of harm than was previously known or recognized) will be immediately reported to the IU IRB and NIH. All severe or life-threatening AEs will be immediately reviewed by the co-PIs and reported to the IU IRB and NIH. All other

AEs will be reported to these entities at the time of continuing review. A summary of AE data (e.g., frequency, types, and corrective actions) will be provided to the IU IRB and NIH at the time of continuing review.

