If an enrolled participant reports having thoughts of being better off dead or of hurting him/herself during any telephone calls (e.g., a scheduling call or a call to the study team initiated by the participant), the exact same procedures as outlined above will immediately be initiated. Please see the Appendix for the full Suicide Management Plan.

Because it is unknown if insomnia therapy (or lack thereof) results in somatic adverse events in antiretroviral-treated HIV-infected patients, we will also carefully document Grade 3 or 4 level toxicities defined using the Division of AIDS Table for Grading Adult Adverse Experiences. Clinical management decisions and decisions to discontinue participants from the trial will be made by the principal investigator(s) in conjunction with the participant’s primary caregiver; care plans and outcomes must be included in the source documentation.

All serious adverse events (SAEs) will be documented on CRFs with unexpected SAEs forwarded to the IU IRB within 10 working days of the event and the remainder to be documented on the annual continuing review.

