If an enrolled participant reports having thoughts of being better off dead or of hurting him/herself during any telephone calls (e.g., a scheduling call or a call to the study team initiated by the participant), the exact same process as outlined above will be initiated. Please see the Appendix for the full Suicide Management Plan.

10.3.2.5 Adverse event financial management, grading, and reporting. In the event of an adverse event, necessary medical and professional intervention will be provided immediately and billed to the participant's medical insurance (if available). If the participant does not have insurance, care will be provided via the indigent care program at Eskenazi Health Hospital. Standard procedures for reporting deviations from protocols will be followed; serious adverse events that meet the Indiana University IRB prompt reporting requirements will be reported within 10 business days. All adverse events will be graded using The Division of AIDS Table for Grading Adult Adverse Experiences is located at: <http://roc.s-3.com/members/download/adulttox.pdf>.

10.3.2.6 Data and Safety Monitoring. Upon discussion with the NIH/National Institutes of Mental Health, this trial is considered a minimal risk study that does not require independent monitoring. As such, only Level 1 monitoring by the co-PIs (Drs. [name] and [name]) is required. The co-PIs under supervision of the IU IRB will meet every 6 months to review and ensure participant safety; monitor recruitment, accrual, randomization, retention, treatment delivery and fidelity; and review data collection and quality; suicidal ideation protection protocol triggers; any adverse events; any protocol deviations; and any IRB amendments. The IU IRB and NIH will receive copies of all monitoring reports and responses at the time of continuing review.

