### 10.6.1 Data and Safety Monitoring Plan (DSMP)

#### 10.6.1.1 Adverse Event Monitoring.

We will systematically identify potential adverse events (AEs): (a) by conducting Eskenazi Health and IUH Health Methodist EMR searches every 6 months for all emergency department visits, outpatient visits, and hospitalizations that occurred among randomized patients and (b) by reviewing responses on a self-report questionnaire assessing for the occurrence of any potential adverse events since the last study visit/call. Any potential AEs spontaneously reported by participants will be evaluated. We will fully investigate, rate, and prepare a Case Report Form for those events that are plausibly related to insomnia, insomnia treatment, suicidal ideation, or any study procedure. For all other captured events (emergency department visits or hospitalizations typically for chronic medical conditions that are unrelated to study involvement), we will provide frequency counts for the SHUTi Intervention and Active Control study arms. We will fully investigate these events only if there is evidence of group imbalance. It is worth noting that that: (a) we are delivering safe and established insomnia interventions, (b) we are not delivering any new or experimental interventions or restricting usual care, and (c) all study procedures are noninvasive (except for the blood draw) and standard.

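### Protocol sections 7.0, 10.3.2.5 and 10.6.1 give inconsistent rules for the reporting deadline, recording and severity grading of adverse events, and the SAP does not settle them

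*Protocol*

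**What the plan says.** **Section 7.0** states "All serious adverse events (SAEs) will be documented on CRFs". Its timing depends on whether the event was expected: the text has "unexpected SAEs forwarded to the IU IRB within 10 working days of the event", while other SAEs are left to the annual continuing review. It names the IRB as recipient and does not mention NIH. It adds that "we will also carefully document Grade 3 or 4 level toxicities defined using the Division of AIDS Table for Grading Adult Adverse Experiences", because it is not known whether treating insomnia, or leaving it untreated, causes somatic events in this population.

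**Section 10.3.2.5** says on timing that "serious adverse events that meet the Indiana University IRB prompt reporting requirements will be reported within 10 business days". Its rule on severity is separate: "All adverse events will be graded using The Division of AIDS Table for Grading Adult Adverse Experiences".

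**Section 10.6.1.1** identifies events through six-monthly searches of the medical record, a self-report questionnaire and spontaneous reports. It then narrows the work: "We will fully investigate, rate, and prepare a Case Report Form for those events that are plausibly related to insomnia". The same goes for events tied to treatment of insomnia, to suicidal ideation or to a study procedure. Other captured emergency visits and hospitalizations are counted by arm and investigated only if the arms look imbalanced.

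**Section 10.6.1.2** rates the plausibly related events on the protocol's own scales. On the four-level severity scale the third level reads "Severe: Inability to perform normal daily activities". Events meeting the IRB prompt-reporting requirements are reported immediately to the IRB and NIH. The next sentence is "All severe or life-threatening AEs will be immediately reviewed by the co-PIs and reported to the IU IRB and NIH". Everything else waits for continuing review.

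**The SAP** has no grading or reporting rule. It covers only totals of emergency visits and hospitalizations.

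**The concern.** The sections overlap in the events they cover but differ in what they require, and none refers to another as the governing rule. Staff who work from 7.0 and staff who work from 10.6.1 could handle the same event differently: a different deadline, a different recipient list, and a CRF with a grade or only an entry in a count.

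The consequence is for safety recording and escalation. Section 7.0 documents Grade 3-4 toxicities precisely because the somatic effects are unknown. A rule that rates an event only once it is judged plausibly related works against that purpose, since an unsuspected effect is the kind least likely to be judged related.

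**Working it through.** No figure in the plan needs recomputing. The check takes four example events through each section. All of the text is current protocol text.

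| Event | Section 7.0 | Section 10.3.2.5 | Section 10.6.1 |
|---|---|---|---|
| A. SAE meeting the IRB prompt-reporting requirements | CRF; if unexpected, to the IRB within 10 working days | Division of AIDS grade; reported within 10 business days; no recipient stated | CRF; functional rating; reported immediately to IRB and NIH |
| B. Expected SAE, plausibly related and rated severe | CRF; annual continuing review | Division of AIDS grade; no deadline, since prompt reporting requires an unanticipated event | CRF; functional rating; immediate co-PI review, and reported to IRB and NIH separately from the events left to continuing review |
| C. Hospitalization that is an SAE, judged not plausibly related | CRF; 10 working days if unexpected, otherwise annual | Division of AIDS grade | Counted in its arm; no rating or CRF; investigated only on imbalance |
| D. Grade 3-4 event, not serious, judged not plausibly related | Documented; no deadline | Division of AIDS grade | No rating or CRF |

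**Deadline (A and B).** The trigger in 10.3.2.5 is an SAE meeting the IRB requirements. The trigger in 10.6.1.2 is any adverse event meeting them. The first class lies inside the second, so every event under 10.3.2.5 carries both deadlines. For B, the sentence in 10.6.1.2 has no expectedness condition, so an event that 7.0 leaves to the annual review is taken out of continuing review by 10.6.1.2.

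**Recording (C and D).** Sections 7.0 and 10.3.2.5 together require a CRF and a grade for C, and documentation and a grade for D. Section 10.6.1 gives both only to plausibly related events. A team following 10.6.1.1 as written will not produce what 7.0 promises. The imbalance that would prompt investigation has no threshold there, in Protocol 9.13.3 or in the SAP.

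**Severity (all rows).** Nothing says how a Division of AIDS grade corresponds to mild, moderate, severe or life-threatening. This matters because *severe* triggers escalation in 10.6.1.2. Event C shows the gap: read literally, the escalation rule covers it if it is severe, but 10.6.1.2 never assigns it a severity.

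**The case against.** The best defence is that these are drafting overlaps in a 50-participant behavioural trial that the protocol calls minimal risk. Several parts of it stand.

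- Ten business days is an outer limit, so immediate reporting satisfies both 10.3.2.5 and 10.6.1.2 for event A. The stated deadlines still differ.
- In the sentence on severe events, *immediately* strictly governs the co-PI review and may not govern the report. Event B therefore shows a difference in handling, without a firm reporting time. The firmer deadline conflict is the preceding sentence of 10.6.1.2 against 10.3.2.5.
- *Serious* and *severe* are different concepts. Section 7.0 sets a deadline for serious events only, and a severe event that is not serious has none there. The conflict in B exists only where the two classes overlap.
- Two scales may both be recorded, and having two is no contradiction. What is missing is the link between them.

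Three stronger readings are tempting, and the documents do not support them.

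- **That unrelated events are missed.** They are not. Section 10.6.1.1 searches for all emergency visits, outpatient visits and hospitalizations among randomized patients. Relatedness governs the rating, full investigation and CRF, and does not govern identification.
- **That one event can range from immediate reporting to annual or unrated.** A prompt-reportable event is by definition unanticipated and at least possibly related, so it should be rated under 10.6.1.2 and should not fall among the expected SAEs left to annual review. Those outcomes belong to different events.
- **That unblinded leads bias a comparison of severity between arms.** No such comparison is planned in Protocol section 9 or the SAP. Who judges attribution is masked, and while Protocol 9.13.5 describes some doctors and the treatment-delivery staff as unblinded, the matching SAP text refers to blinded PIs. No section says whether the person judging attribution is blinded.

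**Conclusion.** The inconsistency is real and worth correcting, within limits. Three things are established from the text:

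1. SAEs meeting the IRB prompt-reporting requirements have two stated deadlines, up to 10 business days or immediate. An expected SAE that is also severe is handled differently in 7.0 and 10.6.1.2, and the recipients differ.
2. For an SAE or Grade 3-4 event judged not plausibly related, whether it is recorded and graded depends on the section followed. This is the most consequential of the three, because following 10.6.1.1 does not deliver what 7.0 requires.
3. Two severity scales are in force with no mapping, and one of their labels triggers escalation.

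The documents give no expected event rates, so the number of affected events cannot be estimated. The effect is on safety recording and escalation. The primary hsCRP analysis is untouched, and no claim of bias between arms is made. The conclusion assumes that *unexpected* in 7.0 and *unanticipated* in 10.6.1.2 mean the same for event A; without that, the conflict between 10.3.2.5 and 10.6.1.2 still holds. Which deadline should govern is for the sponsor and the IRB to settle.

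**What to change.** Reconcile sections 7.0, 10.3.2.5 and 10.6.1 in one table, placed in section 7.0 and referred to from the others. It should give:

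- one severity scale, or an explicit mapping from Division of AIDS grades to the four functional levels;
- one deadline and one recipient list for each event class;
- separate definitions of *serious* and *severe*, so that each rule names the one it means.

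Align 10.6.1.1 with 7.0 so that SAEs and Grade 3-4 events are recorded and graded in both arms whatever their attribution, with attribution judged separately. If the imbalance trigger is kept, state what counts as imbalance.

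The cost is protocol wording plus a small number of CRFs and grades that sections 7.0 and 10.3.2.5 already promise. Treatment, sample size and the efficacy analyses do not change.

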#### 10.6.2 Data and Safety Monitoring Board (DSMB)

For this phase II trial, upon discussion with the NIH/National Institutes of Mental Health, this trial is considered a minimal risk study that does not require independent monitoring. As such, only Level 1 monitoring by the co-PIs (Drs. [name] and [name]) is required. Every six months, a written report will be prepared describing study updates; participant recruitment, accrual, randomization, and retention; treatment delivery and fidelity; data collection and quality; suicidal ideation protection protocol triggers; any adverse events; any protocol deviations; and any IRB amendments. The IU IRB and NIH will receive copies of all monitoring reports at the time of continuing review.

#### 10.7 Inclusion of Women and Minorities

There are no exclusion criteria based on sex, racial category, or ethnicity in the proposed studies. Based on our previous cumulative experience and the general HIV-positive population cared for at the study sites at the Indiana University Health Medical Center (Eskenazi Health Hospital, IU Health Methodist Hospital), it is anticipated that approximately 25% of the study participants will be women.

It is also anticipated that approximately 50% and 5% of the study participants will be black and Hispanic, respectively. American Indians, Alaskan Natives, Asians, Native Hawaiians or Other Pacific Islanders are not expected to be represented in the proposed study population due to extremely low representation of these groups within the HIV outpatient clinics of Eskenazi Health and Indiana University Health Methodist Hospitals and in Indianapolis in general.

#### 10.8 Inclusion of Children and Inclusion across the Lifespan

Participants under the age of 18 are excluded from the proposed studies as inflammation and monocyte activation markers may be affected by hormonal fluctuations during puberty. In addition SHUTi has not been fully evaluated yet in those under 18 years. However, there will be no upper age exclusion to ensure that older participants that are now more representative of the aging HIV population in the United States are included in this trial.

## Appendix: Suicide Management Plan

Suicide management plans very similar to the one described below have previously been approved by the Indiana University IRB and were successfully implemented in prior depression trials conducted by our team (e.g., IRB #'s 1409114254 and 1411802537). Those suicide management plans were constructed with input from Eskenazi Midtown Community Mental Health Center leadership, who concluded that the plans provide a high level of protection while minimizing disruption to usual clinical activities. In the present trial, we will assess suicidal ideation with the PHQ-9 at Entry, Week 12, and Week 24, and we are prepared to appropriately handle the situation should one of the enrolled patients exhibit suicidal ideation.

### (a) In-Person Study Visits

Suicidal ideation will be assessed using Item #9 of the PHQ-9 at Entry, Week 12, and Week 24. If a participant reports having thoughts of being better off dead or of hurting him/herself (i.e., responds with a 1, 2, or 3 to PHQ-9 Item #9 or spontaneously reports suicidal ideation) during any of the Study Visits, the visit will be immediately stopped, and the study coordinators running these visits will interview the participant to complete the Patient Suicidality Form (see below). If the potential participant answers “no” to the clarifying question, the visit will proceed as normal. If the potential participant answers “yes” to the clarifying question, the participant will be asked the three suicide questions.

The study coordinators have been trained by [name], a clinical psychologist, in conducting the interview to complete the Patient Suicidality Form and in following this protocol. [name] will also serve as the primary supervisor to these study coordinators when it comes to their tasks related to this suicide management plan. In [name] completed depression trials (IRB #'s 1409114254 and 1411802537), he has trained various research assistants to effectively conduct this interview and provide a high degree of protection to patients.

The graduate student research assistants are doctoral students enrolled full-time in IUPUI’s clinical psychology Ph.D. program, which is accredited by the American Psychological Association and of which [name] is a core member. The research assistants have completed graduate coursework in psychological assessment, psychological interventions, psychopathology, and ethics and have acquired supervised clinical experience in local healthcare settings. The graduate student research assistants have also been trained by [name] in conducting the interview to complete the Patient Suicidality Form and in following this protocol. [name] is also the primary supervisor of graduate student research assistants.

It is worth noting that neither the study coordinators nor the graduate student research assistants will be making any decisions regarding how to handle a situation. Instead, they will collect information by administering a highly structured, 4-question interview (Patient Suicidality Form, found below) and will follow the straightforward, step-by-step protocol described in the next paragraph. They will be instructed to call [name] if they are unsure about a participant’s response to any of the three questions.

If the participant answers “no” to all three suicide questions or if the patient answers “yes” only to Question 3 (previous attempt) and the most recent attempt was  $\geq$  10 years ago, the visit will proceed as planned, and the completed Patient Suicidality Form will be given to [name].

If the participant answers “yes” to any of the three questions (for Question #3 the previous attempt must be within the past 10 years), the study coordinators or the graduate student research assistant will immediately stop the visit, will contact Drs. [name] and/or [name], and will stay with the participant until a decision is made. If clinically indicated (e.g., the situation is an emergency), a graduate student research assistant and/or [name] will go to the visit location (Infectious Diseases Research Clinic or ICRC) to assist the study coordinators.

Drs. [name] and/or [name] will review all cases screening positive for suicidal ideation immediately to determine the appropriate course of action – e.g., interview the patient to obtain further information, immediately contact the patient’s HIV provider or clinical social worker to involve them in the decision-making process, consult with clinicians at the Eskenazi Health Midtown Community Mental Health Center or with the associated psychiatrist to LifeCare clinic to aid in the decision-making process, escort the patient to the Eskenazi Health Crisis Intervention Unit (‘warm handoff’), and/or contact the police if the patient is at imminent danger of harm and is refusing all care. Either [name] or [name] will also call the participant’s HIV provider notifying him/her of the situation if the provider was not involved in the decision-making process. Regardless of the exact course of action, the study team will ensure that the participant is connected to the appropriate existing clinical services. If the patient’s HIV provider no longer believes that the patient is appropriate for this trial following this situation, the patient will be withdrawn from the trial.

Of note, because patients exhibiting active suicidal ideation are not eligible for this trial, we expect that it will be a rare occurrence that an enrolled patient will screen positive for suicidal ideation.

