##### 4.2 Exclusion Criteria

- 4.2.1 Inability to complete written, informed consent.
- 4.2.2 Inability to read and understand English as seen on a computer screen.
- 4.2.3 Incarceration at the time of any study visit.
- 4.2.4 Active suicidality at Entry, as determined by the patient's HIV provider or social worker following a positive response (1, 2, or 3) to PHQ-9 Item #9 and a positive response (yes) to one or more of the three questions (for Question #3, the previous attempt must be within the past 10 years) on the Patient Suicidality Form (see Appendix).
- 4.2.5 Diagnosed disease or process, besides HIV infection, associated with increased systemic inflammation (including, but not limited to, systemic lupus erythematosus, inflammatory bowel diseases, or other collagen vascular diseases).

NOTE: Hepatitis B or C co-infections are NOT exclusionary, but treatment for hepatitis C cannot be provided during study participation.

- 4.2.6 End stage renal disease requiring renal replacement therapy (dialysis, transplantation).
- 4.2.7 Known or suspected malignancy requiring systemic treatment within 180 days of the Entry Visit.

NOTE: Localized treatment for skin cancers is not exclusionary.

- 4.2.8 Therapy for serious medical illnesses within 14 days prior to the Entry Visit.

NOTE: Therapy for serious medical illnesses that overlaps with a study visit will result in postponement of that study visit until the course of therapy is completed; postponement outside of the allowed study visit timeframe will result in study discontinuation.

- 4.2.9 Pregnancy or breastfeeding during the course of the study.
- 4.2.10 Receipt of investigational agents, cytotoxic chemotherapy, systemic immunosuppressive therapies, systemic glucocorticoids (of any dose), or anabolic steroids at the Entry Visit.

NOTE: Physiologic testosterone replacement therapy or topical steroids is not exclusionary. Inhaled/nasal steroids are not exclusionary as long as the participant is not also receiving HIV protease inhibitors.

- 4.2.11 Active drug use or dependence that, in the opinion of the investigator, would interfere with adherence to study requirements.
- 4.2.12 History of bipolar disorder or a psychotic disorder, including schizophrenia.

NOTE: Depressive disorders are not exclusionary.

- 4.2.13 Current sleep disorder diagnosis other than insomnia disorder (e.g., sleep apnea).

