### Clarifying Question

***Over the past 2 weeks, have you been having thoughts of hurting yourself in some way?***

Yes \_\_\_\_\_ No \_\_\_\_\_  
(Continue) (Stop, no SMP trigger)

Comments:

\*\*\*\*\*

***I'm going to ask you a few questions that are part of the study protocol, because we have seen that in some patients with these symptoms, these are important concerns.***

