#### ***3. Have you attempted suicide in the past?***

Yes \_\_\_\_\_ No \_\_\_\_\_

If YES, in what year was the most recent attempt? \_\_\_\_\_

Comments:

If the patient answers "yes" to any of the three questions (for Question #3 the previous attempt must be within the past 10 years), you must carefully follow the procedures described in the Suicide Management Plan.

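### Appendix (a) and the Patient Suicidality Form stop after a no to a narrower clarifying question, with no stated investigator hand-off and past attempts unasked, while the protocol body goes straight to the three suicide questions

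*Protocol*

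**What the plan says.** The trigger is the same throughout the protocol: item 9 scored 1, 2 or 3, or ideation reported spontaneously. Appendix (a) describes this as a participant who "reports having thoughts of being better off dead or of hurting him/herself". Item 9 is asked at Entry, Week 12 and Week 24.

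Sections 7.0 and 10.3.2.4 then have the research assistant complete the Patient Suicidality Form and give rules only for its three suicide questions. With three negative answers, or only an attempt at least 10 years ago, the visit continues and the principal investigator receives the form. Any other positive answer means immediate contact with the investigators. Neither section mentions a clarifying question. Exclusion 4.2.4 also names only item 9 and "a positive response (yes) to one or more of the three questions", with an attempt counting if it was within 10 years.

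Appendix (a) adds a step. If the answer is no "to the clarifying question, the visit will proceed as normal"; if it is yes "to the clarifying question, the participant will be asked the three suicide questions". On the form, the clarifying question covers the past two weeks and reads "have you been having thoughts of hurting yourself in some way". The instruction under its no box is "Stop, no SMP trigger". The past-attempt item, "Have you attempted suicide in the past", is Question 3 and comes later. Once the three questions have been asked and the result is low risk, Appendix (a) says "the visit will proceed as planned, and the completed Patient Suicidality Form will be given to" a named person.

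**The concern.** The trigger covers two kinds of thought and the clarifying question covers one. A participant who thinks about being better off dead, but not about hurting themselves, can truthfully score positive on item 9 and then truthfully answer no. The Appendix and form then end the interview. No one is told to pass the form on, and whether there has been a recent attempt is never learned.

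A participant with passive ideation and a recent attempt could thus leave any of the three visits without a stated look by an investigator. At Entry, the information that 4.2.4 takes from Question 3 would be missing for that person. The body sections, as worded, would handle the same participant differently.

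**Working it through.** No arithmetic applies: the plan gives no rate of positive item 9 or of negative clarifying answers. The check is to follow one participant through each text. Take item 9 = 1, thoughts of being better off dead, no thoughts of self-harm, and an attempt five years ago (a hypothetical case inside the 10-year window).

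| Step | Sections 7.0 and 10.3.2.4, as worded | Appendix (a) and the form |
|---|---|---|
| Item 9 positive | Visit stops, interview starts | Visit stops, interview starts |
| Clarifying question | Not mentioned | Asked; truthful answer is no |
| Question 3 (past attempt) | Asked; answer is yes, within 10 years | Not reached |
| Investigator | Contacted immediately; review no later than the same day | No contact or hand-off stated |
| Visit | On hold pending review | Continues |

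Change the case so that there is no past attempt. The body sections still send the completed form to the principal investigator. The Appendix and form still state no destination for it. The difference therefore does not depend on the attempt history.

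The other in-person routes all have a destination. A yes to the clarifying question followed by low-risk answers sends the form on, and any other positive answer leads to immediate contact. The clarifying no is the only route without one.

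Four other provisions might close the gap:

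- **Investigator review of positive screens.** Appendix (a) later says the investigators immediately review everyone who screens positive for suicidal ideation. Item 9 is the screen, so a literal reading covers this participant. But the sentence follows the paragraph on a yes to any of the three questions, and the form marks a clarifying no as not triggering the plan. The text is ambiguous, and the form is what the coordinator holds.
- **Staff judgement.** Appendix (a) says interviewers make no decisions and follow the script. Its instruction to call when unsure covers the three questions, although the same paragraph describes a four-question interview.
- **Advice at PHQ-9 of 10 or more (Sections 3.3 to 3.5).** This depends on the total score, not item 9, and leaves the participant to act.
- **Adverse-event rating (Sections 10.6.1.1 and 10.6.1.2).** Events plausibly related to suicidal ideation are rated, but nothing says that a clarifying no is recorded as such an event.

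None of the four clearly supplies the missing hand-off.

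**The case against.** The strongest defence is that this is a deliberate, legitimate tiering. Exclusion 4.2.4 is aimed at active suicidality, and a question about self-harm separates active from passive thoughts. The Appendix says very similar plans were approved by the institutional review board and built with input from mental-health-centre leadership. Interviewers are trained and supervised by a clinical psychologist. Sections 7.0 and 10.3.2.4 also send the interviewer to the form, so the clarifying step could be read into them. All of this stands as a defence of having a clarifying step. It does not explain why this one outcome has no destination when low-risk outcomes further along do.

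It can also be said that handing over the form does not itself reveal a recent attempt, because Question 3 is still blank. That is correct. The hand-off puts the positive item 9 before someone with authority to ask; only a change to the questions would collect the answer routinely.

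Two stronger readings are tempting. A reader might infer that 4.2.4 cannot be assessed at Entry, or that actively suicidal people would be randomised. The documents do not support that: on the form's own logic, someone without a yes to the three questions does not meet the criterion. What is missing is one input, the past-attempt answer, for people who stop early. A reader might also count branches and treat the share without a hand-off as the size of the problem. The count depends on how the low-risk sentence is split, and says nothing about how many participants take each branch.

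**Conclusion.** The point holds as a participant-safety clarification. The body and the Appendix with its form describe different pathways after a positive item 9. Followed as printed, the Appendix version lets a participant with passive ideation and an attempt within 10 years finish the visit with no clearly stated investigator review. At Entry the Question 3 element of 4.2.4 is not collected for that person.

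This rests on two assumptions: coordinators follow the form literally, and participants answer the clarifying question as worded. The number affected cannot be estimated from the documents. It is probably small, since the Appendix expects positive screens among enrolled participants to be rare. Sample size, power and the hsCRP analysis are unaffected.

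**What to change.** 1. In Appendix (a), after a no to the clarifying question, and beside the stop instruction on the form, add: *give the completed form, with the item 9 score noted, to the principal investigator before the participant leaves*. The investigator can then decide whether Question 3 should be asked. This extends the plan's existing low-risk hand-off and adds the timing.
2. In Appendix (a), extend the call-if-unsure instruction from three questions to all four.
3. Resolve the body/Appendix conflict in the protective direction. Either add thoughts of being better off dead to the clarifying question, or ask Question 3 after any positive item 9. The latter changes the tiering and is the investigators' choice. Do not align the texts by writing into 7.0, 10.3.2.4 or 4.2.4 that the three questions follow only a yes; that would carry the narrower gate into sections that do not now state it.

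The cost is a few lines of text, a short staff note, and a few extra forms for the principal investigator to read. Item 3 also adds a question or a phrase to the interview. No design or analysis change is needed.
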